# 5 Human Subjects

# 5.1 Subject Population

The maximum tolerated dose (MTD) 3+3 design encompasses blocks of 3 patients allocated to dosing schematics. In this study, we have 4 dosing schematics to be tested. Therefore, a minimum number of 6 and maximum number of 12 patients will participate in this trial.

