# 1 Protocol Overview

Study Description	The purpose of this study is to identify a tolerable dose for postpartum ketamine infusion using a maximum tolerated dose (MTD) 3+3 design. A loading dose over 1 hour will be the MTD variable to be tested, as our data suggest that ketamine side effects occur with the loading dose.
Study Population:	Patients having cesarean delivery (CD) who are either: 1) planning not to breastfeed; or 2) are receiving ketamine as part of clinical care, will be enrolled. Ketamine will be started in postpartum patients, after cord clamping.
Planned Sample Size:	The projected sample size will be a maximum of 12 patients with complete primary outcome data within the MTD 3+3 design.
Participating Institutions (if a multicenter clinical trial)	N/A

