# 3.4 Endpoints

# 3.4.1 Primary Endpoint

Maximum Tolerated Dose (MTD). The MTD will be defined as the dose at which fewer than 33% of patients experience a DLT defined by intolerability.

Tolerability (dichotomous Yes/No)

Tolerability (YES) will be defined as: lack of adverse events (adverse event defined as: severe unresolved hemodynamic effect: systolic blood pressure <80 or >160, heart rate <40 or >120).

Lack of Tolerability will be defined as presence of any adverse event (i.e., severe unresolved hemodynamic effect: systolic blood pressure <80 or >160, heart rate <40 or >120).

A **DLT** event is defined by complete infusion cessation due to intolerable side effect acceptability ratings by patient, OR the experience of an intolerable event as defined above. The escalation of dosing will be as noted in Figure 2 and is based on a modified Fibonacci sequence  $^{101,102}$  with smaller proportional increases in dose in the escalation scheme. Escalations occur until 2 in a cohort of 3 to 6 experiences DLT (i.e., until  $\geq$ 33% of patients experience DLT at that dose). The dose **below** this level estimates the MTD.

Participants will be classified as having had a DLT if any of the following conditions are met:

- Persisting (i.e., unresolved after 3 consecutive measurements within a 15-minute interval)
  hemodynamic side effects defined as below and despite treatments or minimizing
  infusion rates as specified.
  - Systolic blood pressure <80 or >160
  - Heart rate <40 or >120
- Complete infusion cessation due to intolerable side effect acceptability ratings by patient

Primary Outcomes will be measured at a minimum of every 4-hours from the start of the ketamine infusion (t = 0) for 24-hours (12-hours post infusion cessation). Additional assessments will be administered between the 4-hour measurements if any adverse event or side effect is noted by the patient.

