# Protocol Overview.

Patients will respond to surveys prior to and following cesarean delivery regarding their current pain and mood. Patients will begin study procedures in the third trimester of pregnancy, within approximately one week of scheduled cesarean delivery, until 12-weeks postpartum.

Preoperative weight and vital signs will be measured, and baseline inventories completed (Figure 1; refer to section 1.1). After delivery, cord clamping and declaration of clinical stability by the anesthesiologist (typically~5-15 min after delivery; ±30 minutes), a loading infusion of ketamine 0.05 mg/kg/hour will begin for the first 3-patients in the study. Vital signs and side effect symptomology will be measured 15, 30, and 60 minutes (±5 minutes) after infusion start, and at 4, 8, 10, 12, 16, and 24 hours (±30 minutes) after infusion start. Plasma samples will be collected at 1, 6, 10, and 12 hours (±30 minutes) after infusion. Any report of adverse events or side effects will trigger a blood draw for analysis and correlation of these symptoms to plasma levels of ketamine within the 12-hour infusion. All assessments have been timed to coincide with timing intervals of typical post-CD clinical care interventions. Patients dosing after the first three patients will proceed based on the MTD protocol in Figure 2; refer to section 1.1.

MTD dosing protocol.

A loading dose and maintenance infusion strategy will be used (Figure 2; in section 1.1). MTD to be tested will focus on the initial loading dose used to achieve a higher plasma concentration in a brief period. Ketamine dose will not exceed sub-anesthetic ranges (≤0.2mg/kg/hr). The maintenance rate of 0.05mg/kg/hr is based on our preliminary data suggesting tolerability, and on data suggesting that this rate might yield adequate plasma concentrations necessary for the treatment of depression. The first set of 3 patients will receive a loading infusion of ketamine 0.05 mg/kg/hr for the first data. The decision to escalate the loading infusion dose, enter 3 more at the same level, or stop, will not occur until 3 patients complete the 0.05 mg/kg/hr protocol. A **DLT** event is defined in section 3.4.1.

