# 11.2 Other Criteria Requiring Discontinuation

Withdrawal of Subjects for reasons other than Non-compliance or Adverse Events:

- Protocol non-adherence: incorrect dosing strategy or other non-adherence points at the judgement of the PI
- Incomplete side effect diary data, defined as missing 20% or more responses

Withdrawn participants will be replaced at a proportion of 1:1. Procedures are as follows:

• Study personnel, investigators, DSMB will be informed of the need for replacement due to participant withdrawal.

Subsequent data to be collected from the withdrawn participant will be restricted to the
minimum amount necessary to continue to monitor safety, i.e., side effect diary including
questions of sedation, LSD short form, dizziness, lightheadedness, bad dreams, nausea,
vomiting, pruritus, hallucinations.

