# 12 Statistical Analysis

By virtue of its design, the maximum tolerated dose (MTD) 3+3 design encompasses a minimum number of 6 and maximum number of 12 patients enrolled in this trial. The results identify the drug dose at which ≥33% of patients experience dose limiting toxicity, which we have defined by unacceptable side effects or adverse events. The number of subjects at each dose is dictated by traditional MTD 3+3 design, balancing the risks associated with the study drug and the assessment of adverse event rates. A formal power calculation was not performed.

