#### 12.2 Sample Size Determination

The number of subjects (minimum of 6; maximum of 12) at each dose is dictated by traditional MTD 3+3 design, balancing the risks associated with the study drug and the assessment of adverse event rates. A formal power calculation was not performed.

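### The stated maximum of 12 patients is 4 levels × 3 and omits the plan's own expansion to 6 per level; the readable escalation rule runs from 3 to 24 evaluable patients

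*Combined protocol and SAP*

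**What the plan says.** **Trial size.** Section 5.1 describes blocks of 3 patients and continues: "In this study, we have 4 dosing schematics to be tested. Therefore, a minimum number of 6 and maximum number of 12 patients". Section 1 gives the ceiling for evaluable patients: "The projected sample size will be a maximum of 12 patients with complete primary outcome data within the MTD 3+3 design". Section 12 gives the same range for enrolled patients: the design "encompasses a minimum number of 6 and maximum number of 12 patients enrolled in this trial". Section 12.2 attaches the range to each dose: "The number of subjects (minimum of 6; maximum of 12) at each dose is dictated by traditional MTD 3+3 design". It adds that there was no formal power calculation.

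**Escalation rule.** Section 4, under the MTD dosing protocol, lists three options once the first three patients have completed: "The decision to escalate the loading infusion dose, enter 3 more at the same level, or stop". Section 3.4.1 says: "Escalations occur until 2 in a cohort of 3 to 6 experiences DLT". The dose below the stopping level estimates the MTD.

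**Replacement.** Section 11.2 says: "Withdrawn participants will be replaced at a proportion of 1:1". Sections 5.5 and 11.1 say the same.

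**The concern.** The derivation in Section 5.1 multiplies levels by block size and leaves out the second block of three that the escalation rule allows at any level. The cap and the rule then cannot both be honoured. Two short examples show this:

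- 0/3, 0/3, 0/3, then 1/3 at level 4. The trial has 12 patients and the rule calls for three more. Under the cap, level 4 stays unresolved.
- 1/3 then 0/3 at level 1, followed by 0/3 at levels 2 and 3. The trial has 12 patients and level 4 is never opened.

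One DLT is enough in each case. The primary endpoint is the MTD, so what is at stake is whether the trial can finish its own search. If the cap is enforced, some trials end before the rule reaches a stopping level. If the rule is followed, the trial can exceed its stated size.

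The stated figures also disagree with each other. The same 6 to 12 is a trial total in Sections 5.1 and 12 but a per-dose number in Section 12.2. The 12 counts patients with complete outcome data in Section 1 and enrolled patients in Section 12; with 1:1 replacement these differ as soon as one patient is replaced.

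**Working it through.** **Inputs.** Four levels and blocks of 3 (Section 5.1, reading the four schematics as four escalation levels). Option to add 3 at the same level (Section 4). Stop at 2 DLTs in 3 to 6 patients (Section 3.4.1). In 3+3 terms: 0/3 escalate; 1/3 add three; 1/6 escalate; 2 or more DLTs stop.

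**Reproducing the plan's figure.** Without expansion: 4 × 3 = 12, which matches exactly.

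**With the plan's own expansion.**

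- Maximum: 4 × 6 = 24. This is reached with 1 DLT in the first three at every level and none in the added three at levels 1 to 3.
- Minimum: 3, when at least 2 of the first 3 have a DLT.
- Smallest trial that names an MTD with a tested level below the stopping level: 3 + 3 = 6.
- Smallest trial that clears all four levels with one expansion: 3 × 3 + 6 = 15.
- Of the 13 outcome paths that end at exactly 12 patients, only 0/3 at all four levels clears level 4. The other twelve stop on DLTs.
- Section 12.2 read literally: 4 × 6 = 24 to 4 × 12 = 48 patients.

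**How often 12 is exceeded.** For DLT probability p at a level:

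- P(0/3) = (1−p)³
- P(1/3, then 0/3) = 3p(1−p)² × (1−p)³
- P(level cleared) = (1−p)³ + 3p(1−p)⁵
- P(all four cleared within 12 patients) = product of (1−p)³ over levels, that is, no DLT at all

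At a constant p = 0.05:

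- P(level cleared) = 0.8574 + 0.1354 × 0.8574 = 0.9734
- without the cap: 0.9734⁴ = 0.898
- with the cap: 0.95¹² = 0.540

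Exact enumeration of all paths gives the table. Every rate is an assumption. The 1/8 (12.5%) in Section 6.3 is the share who received a reduced infusion rate, and the plan itself calls those data unrepresentative, so 12.5% is only one illustrative value.

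| DLT rate, levels 1–4 | P(N>12) | of which rule stops after patient 12 | P(clear level 4), no cap | P(clear level 4), cap 12 | Expected N, no cap |
|---|---|---|---|---|---|
| 5% flat | 38% | 2% | 90% | 54% | 13.1 |
| 12.5% flat | 46% | 10% | 55% | 20% | 12.5 |
| 20% flat | 32% | 14% | 25% | 7% | 10.7 |
| 30% flat | 14% | 9% | 6% | 1% | 8.0 |
| 5/10/15/20% | 51% | 20% | 51% | 20% | 13.5 |
| 5/10/20/33% | 50% | 32% | 27% | 10% | 13.4 |
| 12.5/20/30/40% | 32% | 25% | 9% | 3% | 11.4 |
| 20/30/40/50% | 15% | 14% | 2% | 0.5% | 9.2 |

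The rest of P(N>12), beyond the third column, is trials that clear all four levels with more than 12 patients.

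**Size of the overrun.** In every scenario more than half of the trials above 12 have exactly 15 patients (31 of 38 percentage points at flat 5%; 34 of 51 at 5/10/15/20%). P(N>18) is 0.6% to 3.0%, and P(N=24) is 0.02% to 0.3%.

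**The case against.** **The dosing figure is not visible.** Sections 3.4.1, 4 and 7 defer to Figure 2, which could limit which levels expand or fix an end point. This stands as a limit: the conclusion covers the readable text only. A restriction in the figure would still have to be reconciled with Sections 3.4.1, 4 and 12.2.

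**Another stopping wording fits 12.** Section 3.4.1 glosses its rule as a DLT rate of at least 33%, and Section 12 repeats that threshold. Since 1/3 = 33.3%, a literal reading stops at one DLT in three, never expands, and tops out at 12. But it contradicts both the option to add three and the stated two DLTs in 3 to 6 patients, and its minimum is 3, not 6. It shows that the passages need reconciling; it does not rescue the stated range.

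**24 is a ceiling, not a forecast.** Correct. The practical overrun is 15, and expected size is 8.0 to 13.5 across the scenarios.

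**The minimum of 6 is defensible.** It is, as the smallest trial that names an MTD with a tested lower level, but it is not labelled so. The contingency in Section 6.3 for an intolerable lowest dose points to Table 1 and Figure 3. The readable Table 1 adjusts dosing within a patient, and no readable text opens a lower cohort.

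**The 12.2 and enrolment points are wording.** They are, and the main finding does not depend on them.

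**Conclusion.** The concern holds. The maximum of 12 is reproduced only by leaving out an expansion that the plan itself allows; with it, the readable rule gives 3 to 6 evaluable patients per level and 3 to 24 in total. Under the assumed DLT rates, a trial following the rule exceeds 12 with probability 14% to 51%, most often by three patients. Enforcing the cap lowers the chance of clearing level 4 in every scenario, for example from 90% to 54% at a flat 5%. The range 3 to 24 and the zero-DLT condition follow from the rule alone. The probabilities rest on assumed rates and independent patients. Everything assumes four escalation levels and no restriction in the unseen Figure 2. This should be corrected because the readable text does not say whether cap or rule governs, or how a capped trial would report its primary endpoint.

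**What to change.** - Restate Sections 1, 5.1, 12 and 12.2 as 3 to 6 DLT-evaluable participants at each of up to 4 levels, 3 to 24 evaluable in total. If 6 is kept as a minimum, label it the smallest trial that yields an MTD with a tested lower level.
- State planned enrolment separately from the evaluable number, because withdrawals are replaced 1:1.
- Detach the 6 to 12 range in Section 12.2 from each dose.
- If the cap of 12 is kept, state that it overrides the rule and that reaching it before the stopping rule is met is reported as MTD not determined, with the highest level cleared.
- Reconcile the threshold of at least 33% with the two-DLT wording and with Figure 2, so that one stopping rule is stated throughout.
- As separate housekeeping, clarify or remove the 24 pharmacokinetic patients in Section 6.4. That number is not used here as support.

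The cost is restated figures in the protocol and the IRB and pharmacy documents, and a higher enrolment ceiling. If the two-DLT rule with expansion is the one intended, the escalation rule itself does not change.

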#### 5.2 Inclusion Criteria

- Cesarean delivery
- Adults 18 years and older
- Term delivery ≥ 37 weeks gestation anticipated at time of delivery
- ASA PS 2 or 3
- •
- \_
- One of the following must be met for inclusion:
  - Not planning to breastfeed
  - o Ketamine use indicated for pain management plan.

#### 5.3 Exclusion Criteria

- Patient going under general anesthesia for cesarean delivery
- Allergy to study medication (ketamine)
- ASA PS 4 +
- Contraindications to neuraxial anesthesia
- Preterm delivery (<37 weeks gestation)

- Anticipated fetal-neonatal complex care plan as indicated in the patient's chart
- Patient history of ketamine or PCP abuse
- Patient history of schizophrenia or psychosis
- Patient history of liver or renal insufficiency
- Patient history of uncontrolled hypertension, chest pain, arrhythmia, head trauma, or intracranial hypertension, uncontrolled thyroid disease, or other contraindications to ketamine
- Participating in another pain intervention trial

- Pre-eclampsia with severe features
- Hemodynamic instability
- Contraindicated medications use:
  - o Oral antihypertensive medications (exclusion: hypertensive disorders of pregnancy)
  - o Intravenous magnesium (exclusion: pre-eclampsia with severe features)
  - Ketamine, phencyclidine, psilocybins, or any other psychedelics (exclusion: ketamine or PCP abuse)
  - Lithium, valproate, carbamazepine, lamotrigine, haloperidol, chlorpromazine, fluphenazine, aripiprazole, clozapine, or other typical or atypical
  - o antipsychotic medications (exclusion: schizophrenia or psychosis)

#### 5.4 Recruitment Methods

The current process for research recruitment is that the research anesthesia team will review charts for all patients presenting for cesarean delivery or who are likely to present for a cesarean delivery in the labor and delivery rooms. Prenatal records will indicate patients planning not to breastfeed. During prenatal anesthesiology evaluations, the anesthesiology team will identify patients who are including ketamine infusion as part of their pain management care. Research staff will contact patients to explain the availability of the study to the patient meeting eligibility criteria.

Additional methods of recruitment include directly approaching potential subjects (in-person), the use of Email/Listserv/Electronic Mailing List, use of Flyers/Posters or Brochures in provider offices and clinics, use of Pitt+Me university research registry portal, and patient/participant referrals.

Patients will be eligible if they are receiving ketamine as part of their clinical care, and these typically include patients with a history of complex pain, history of chronic pain with or without treatment, current everyday smokers, patients with opioid or substance use disorder, and patients who have a documented history of treated or untreated anxiety, depression, or trauma.

Eligible patients will be notified of their eligibility to participate in the study by clinical and research staff. Should the patient wish to hear more, the study coordinator will discuss study participation. Questions will be answered, and time will be afforded to patients per the Informed Consent Procedures outlined, to minimize risks of coercion or undue influence.

Upon completion of the baseline inventories and the ketamine infusion and blood collection, patients will receive a payment of \$750 (see Appendix 4 for payment details). Upon completion of the postpartum weekly surveys, payments of up to \$150 will be made at both 6- and 12-weeks postpartum.

*In-Hospital Encounter*Baseline inventories

Complete infusion and all blood draws	\$ 750.00
Postpartum Encounters	
Complete all weekly surveys @ \$25.00/week	
Complete weekly surveys for 6 weeks	up to \$150.00
Complete weekly surveys for weeks 7-12	up to \$150.00
Grand Total	\$ 1,050.00

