# Patient Reported Side Effects Dose Delays or Adjustments

[figure not shown]
- Side Effect Acceptability ratings are defined in section 3.4.2. Patient reported side effects (i.e., dizziness, lightheadedness, bad dreams, nausea, vomiting, itchiness, and hallucinations: all are dichotomous outcomes). These side effects will be evaluated based on patient-specific reports of how "acceptable" or "unacceptable." Patients reporting side effects and rating them as "unacceptable" will follow the dose delay or adjustment described in the Table 1. If side effects are rated "acceptable" then no dose delays or adjustments will occur.
- Figure 3 Decision Chart for Acceptability Based dose revisions.

Table 1. Loading and Maintenance Dose Adjustment Procedures:

Systolic blood pressure <80 or >160, Heart rate <40 or >120  Monitor for 5 minutes minutes for symptom resolution  Monitor for 5 minutes for symptom resolution  If event does not resolve  Hold infusion for 5 box (e.g., 0.05mg/kg/hr) and continue infusion.  If event does not resolve  Hold infusion for 5 box (e.g., 0.05mg/kg/hr) and continue infusion.  May D/C infusion and monitor subject for safety as	Event	1st Action	2 nd 1	Action	3rd /	Action	If event does not resolve
Pressure <80 or >160,   Heart rate <40 or >120   Heart rate <40 or >1							
monitor subject for safety as described in Section 7.4 and described in Section 7.4 and 7.5  Event qualifies as DLT	pressure <80 or >160,	labetalol or hydralazine per managing anesthesiologist Monitor for 5 minutes for symptom	for 5 minutes - symptom recheck at 5	(e.g., 0.05mg/kg/hr reduced to 0.025 mg/kg/hr) and continue	for 5 minutes - symptom recheck at 5 minutes:  May D/C infusion based on investigator discretion and monitor subject for safety as described in Section 7.4 and	(e.g., 0.025mg/kg/hr reduced to 0.013 mg/kg/hr) and continue	minutes of unresolved hemodynamic effect:  D/C infusion and monitor subject for safety as described in Section 7.4 and 7.5  Event qualifies

Event	1st Action	2 nd A	Action	3rd A	Action	If event does not resolve
		If event does not resolve	If the event resolves	If event does not resolve	If the event resolves	 1650.776

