Appendix 4. Participant Payment per Task

		PREPARE 1	Payment						
Patient Tasks	Timing	Payment	Patient Tasks	Timing	Payment				
Baseline Sur	rveys		Postpartum Surveys						
Prior to c	lelivery	\$60		Week 1	\$25				
				Week 2	\$25				
Infusion Pay	yments			Week 3 \$25					
Plasma	Samples (12	ml of blood)		Week 4 \$2					
	T 1 hour	\$62.50		Week 5	\$25				
Infusion	T 6 hour	\$62.50		Week 6	\$25				
nfu	T 10 hour	\$62.50		Week 7					
I	T 12 hour	\$62.50		Week 8	\$25				
	Total	\$250.00		Week 9	\$25				
				Week 10	\$25				
Side Effe	ct Diaries			Week 11	\$25				
Infusion	T 1 hour	\$50.00		Week 12	\$25				
	T 6 hour	\$50.00							
	T 10 hour	\$50.00		Total	\$300				
I	T 12 hour	\$50.00							
	T 16 hour	\$50.00							
t- ion	T 20 hour	\$50.00							
Post- Infusion	T 24 hour	\$50.00							
I	T 12 hour	\$50.00	GRA	AND TOTAL	\$1,050				
	Total	\$400.00							
Vital Signs	6								
	T 1 hour	\$5.00							
Infusion	T 6 hour	\$5.00							
	T 10 hour	\$5.00							
$\Gamma$	T 12 hour	\$5.00							
	T 16 hour	\$5.00							
Post- Infusion	T 20 hour	\$5.00							
	T 24 hour	\$5.00							
	T 12 hour	\$5.00							
	Total	\$40.00

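### Section 5.4 ties the $750 in-hospital payment to completing the infusion, Appendix 4 pays the same $750 by task, and stopping for intolerable ratings is a DLT

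*Combined protocol and SAP*

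**What the plan says.** Section 5.4 states the in-hospital payment twice. The text makes $750 due "Upon completion of the baseline inventories and the ketamine infusion and blood collection" and points to Appendix 4 for details. The table below it sets $750.00 against "Complete infusion and all blood draws", under the in-hospital heading that also lists the baseline inventories. The two survey lines in that table are worded as maxima of $150 each; the $750 is a fixed sum.

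Appendix 4, headed "Participant Payment per Task", allocates the in-hospital money to baseline surveys, four plasma samples, eight diary lines and eight vital-sign lines. No line is for completing the infusion.

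Section 3.4.1 defines two DLT routes. One is persisting blood pressure or heart rate outside fixed limits. The other is "complete infusion cessation due to intolerable side effect acceptability ratings by patient". Table 1 in Section 6.3 also labels unresolved sedation or low respiratory rate as a DLT.

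Under Section 6.3, side effects rated acceptable lead to no hold or reduction, and those rated unacceptable enter the Table 1 sequence of holds, reductions and, if unresolved, discontinuation.

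**The concern.** Two sections state different conditions for the same $750, and nothing says which governs. The 5.4 condition touches the primary endpoint. One DLT route runs through the patient's own ratings and ends in stopping the infusion, and 5.4 makes payment conditional on not stopping. A patient who knows that condition has a monetary reason to call a side effect acceptable, or to carry on.

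The direction of any resulting error is clear: fewer patient-driven DLTs and a higher selected MTD. The trial has at most 12 patients and escalates until 2 in a cohort of 3 to 6 have a DLT, so one undeclared event can reverse a decision.

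The version history places the addition of the rating-based route in version 7.0. The payment-plan edits that it names are in versions 2.0 and 3.0. The payment wording may therefore not have been checked against the present DLT definition.

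**Working it through.** **1. The plan's own total.** From Appendix 4:

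- baseline surveys: $60
- plasma: 4 × $62.50 = $250
- diaries: 8 × $50 = $400
- vital signs: 8 × $5 = $40

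The sum is 60 + 250 + 400 + 40 = $750. Adding 12 weekly surveys × $25 = $300 gives $1,050. Both match Section 5.4, so tasks other than infusion completion account for the whole $750.

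**2. Amount that depends on not stopping.**

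- *Section 5.4 read literally:* up to $750, or 750 − 60 = $690 if the baseline item is still paid.
- *Appendix 4:* $0 for completion itself. Baseline, diaries and vital signs come to 60 + 400 + 40 = $500, and none of these needs a running infusion. Section 7.5 continues diaries and vital signs after the infusion stops.
- *Plasma draws under Appendix 4:* unsettled. The opening of Section 7 places the draws during the infusion, and Section 11 restricts data after withdrawal to safety items without listing plasma. On the other side, the sampling paragraph of Section 7 times the draws from infusion start and wants them for relating DLTs to PK parameters.

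If draws after a stop are neither taken nor paid (assumption):

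| Infusion stops | Draws lost | Loss |
|---|---|---|
| before the 1 h draw | 4 | 4 × 62.50 = $250 |
| between 1 h and 6 h | 3 | $187.50 |
| between 6 h and 10 h | 2 | $125 |
| between 10 h and 12 h | 1 | $62.50 |

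This range covers draws only. It assumes that diary and vital-sign tasks run to 24 h from infusion start, as Section 3.4.1 and Appendix 2 schedule them.

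**3. How one event matters.** In a cohort of six, 2/6 = 33% stops escalation and 1/6 = 17% does not.

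**4. Illustration of sensitivity (not an estimate).** Take the usual 3+3 rule: pass with 0/3, or with 1/3 followed by 0/3. With DLT probability p, the chance of passing a level is (1 − p)³ + 3p(1 − p)⁵. If a share s of all DLTs goes undeclared, replace p by p(1 − s).

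| True p | s = 0 | s = 10% | s = 25% | s = 50% |
|---|---|---|---|---|
| 0.20 | 0.709 | 0.752 | 0.814 | 0.906 |
| 0.33 | 0.434 | 0.500 | 0.605 | 0.783 |
| 0.50 | 0.172 | 0.234 | 0.351 | 0.600 |

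The documents give neither p nor s. Only patient-rated DLTs can go undeclared for this reason, so s cannot exceed their share of all DLTs.

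**The case against.** The strongest reply is that Section 5.4 is a summary that sends the reader to Appendix 4, and Appendix 4 has no completion item. The 5.4 table also uses the word complete for the weekly surveys, which are paid at $25 each. The largest item, $400, pays for filling in the diary, where side effects are reported, whatever the answers. The consent form is not in the copy reviewed and may already prorate payment.

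Much of this stands. It defeats three stronger readings that a reader might infer:

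- *A patient who stops forfeits $750, or 750/1,050 = 71% of the total.* Appendix 4 contradicts this. The sum at risk there is at most the draws.
- *A patient loses money by rating a side effect unacceptable.* Table 1 starts with a hold and, if the event resolves, continues at a reduced dose. A patient can give that rating and still finish the infusion. The DLT in Section 3.4.1 is the cessation, not the rating.
- *The MTD will be biased upward by a known amount.* The documents give no share of patients who would persist, and measured or staff-assessed DLTs are outside the incentive.

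The reply does not remove the conflict. Section 5.4 states its completion condition in both text and table, without the maximum wording that it uses for the surveys. Appendix 4 does not say what an early stopper receives.

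**Conclusion.** The point holds as a conflict between two stated payment conditions. One of them, if followed, would discourage the patient-driven stopping that counts as a DLT. The direction is toward fewer patient-driven DLTs and a higher MTD; the size cannot be estimated from the documents.

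The exposure is up to $750 under the literal 5.4 wording. Under Appendix 4 it is $62.50 to $250, and only if later draws are neither taken nor paid after a stop. The point deserves correction because the trial is small, one event can change an escalation decision, and the correction is nearly free.

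**What to change.** In Section 5.4, replace the completion line in the table and the matching sentence with the Appendix 4 per-task amounts, worded as up to $750. State in 5.4 and Appendix 4, and make the consent form agree, that no payment depends on completing the infusion, on any acceptability rating or on having a DLT. State that a participant whose infusion stops early for side effects is still paid for the remaining scheduled draws, diaries and vital signs.

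While editing Appendix 4, check its time points. It lists 12 h twice for diaries and vital signs, and pays for a 6 h diary that Appendix 2 does not schedule.

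The cost is wording plus at most $250 per early stopper, within the $750 already set per participant. No dose or clinical rule changes.
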